11.5.3 Stable Disease (SD)

Stable disease is defined as less than a PR (see above) but is not progressive or relapsed disease FDG-avid or PET positive prior to therapy: PET positive at prior sites of disease and no new sites on CT or PET. Variably FDG-avid or PET negative: no change in size of previous lesions on CT

11.5.4 Progressive Disease (PD) or Relapsed Disease (RD):

1. Appearance of a new PET positive (Deauville 4 or 5) lesion(s) > 1.5 cm in any axis, $\geq 50\%$ increase in SPD of more than one node, or $\geq 50\%$ increase in longest diameter of a previously identified node > 1 cm in short axis..
2. $>50\%$ increase from nadir in the SPD of any previous lesions

New sites of FDG-avidity felt unrelated to lymphoma (Deauville 3 or less) not be considered PD or ED, but imaging should be repeated 6-8 weeks later to insure resolution of inflammatory changes.

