10.3 Post Treatment Evaluations

- Subjects without progression will be seen every 3 months for the first 2 years with CT scans every 6 months. After 2 years, subjects will be seen every 6 months with CT scans annually through 5 years.

- Hematology: CBC with differential
- Serum chemistries: Na, K, Cl, HCO₃, glucose, blood urea nitrogen (BUN), creatinine, calcium, magnesium, phosphate, total bilirubin, AST, ALT, alkaline phosphatase, albumin, and total protein.
- Brief physical examination
- Vital signs, including weight, temperature pulse, blood pressure, respiratory rate, and oxygen saturation
- ECOG Performance Status;
- Recording of AEs (patients and/or family members will be instructed to telephone the site with any changes in mental or physical status or with any questions regarding treatment)
- Recording of concomitant medications.
- Contrast enhanced CT scan of the chest, abdomen, and pelvis with tumor measurements will be performed every 6 months (+/- 7 days) beginning 6 months following the end of treatment restaging scan for two years and then annually through 5 years or until disease progression

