4. PET/CT Scan will be performed at baseline, 6 weeks after completion of the first cycle, and 6 weeks after completion of the second cycle. Staging will then be performed with CT scans of the chest, abdomen, and pelvis every 6 months for the first 2 years and then annually for 5 years or until progression. Neck CT after baseline study is only required if neck was involved on baseline imaging.
5. Hematology –Hematology should be performed at baseline, weekly during cycle 1 and 2, every 3 months during follow up, and at the time of study treatment completion
6. Coagulation –The coagulation profile must be performed at baseline only and repeated only as clinically indicated
7. Biochemistry –Biochemistry should be performed at baseline, weekly during cycle 1 and 2, every 3 months during follow up, and at the time of study treatment completion. Subjects will have hepatitis serologies, LDH, and beta-2 microglobulin drawn at baseline.
8. Peripheral blood flow cytometry for calculation of absolute b and t lymphocytes should be performed at baseline and on day 8 of cycle 1.
9. Serum pregnancy test –All females of childbearing potential should complete a serum pregnancy test within 7 days prior to the administration of blinatumomab on day 1 of cycle 1. The test will be repeated on day 1 of cycle 2.
10. Prior/concomitant medications –Record all medications administered \leq 30 days prior to the administration of blinatumomab. Record all medications taken during the study on the Concomitant Medications eCRF.
11. Adverse events –. Subjects must be instructed to notify the investigator concerning any undesirable symptoms or side-effects while on study. Adverse event monitoring should be continued for at least 4 weeks following the last dose of study treatment. Antineoplastic therapies since discontinuation of study drug – All cancer medications/therapies given to a subject after the last dose of study drug must be recorded in the Antineoplastic therapies since discontinuation of study drug eCRF. This should be done monthly for the first 6 months, then once every 3 monthly thereafter until disease progression or subject receives new antineoplastic therapies whichever happens first.

12. Subjects without progression will be seen every 3 months for the first 2 years with CT scans every 6 months. After 2 years, subjects will be seen every 6 months with CT scans annually through 5 years.

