11. MEASUREMENT OF EFFECT

11.1 Antitumor Effects

Response and progression will be evaluated in this study using the modified Cheson criteria for lymphoma response.(14)

- Patients will be assessed for response at 6 weeks after the conclusion of cycle 1 (within 7 days of day 84) using a CT scan of the chest, abdomen and pelvis, as well as a full body PET scan (preferably a combined modality PET-CT scan will be used). Neck CT only required if involved on baseline imaging.
- Patients who continue on study (non-progressors) will be re-evaluated at 6 weeks after the conclusion of cycle 2 (within 7 days of day 168) using a CT scan of the chest, abdomen and pelvis, as well as a full body PET scan (preferably a combined modality PET-CT scan will be used). Neck CT only required if involved on baseline imaging.
- Patients who continue on study (non-progressors) after 2 cycles will be assessed using a CT scan of the chest, abdomen and pelvis every 6 months for 2 years and then annually for 5 years or until progression. Neck CT only required if involved on baseline imaging.

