11.5 Response Criteria

11.5.1 Complete Response (CR)

CR requires **all** of the following:

1. **PET positive prior to therapy:** mass of any size permitted if PET negative with a score of 3 or less on the Deauville five point scale.

1-no uptake or no residual uptake

2-slight uptake, but below mediastinal blood pool

3-uptake above mediastinal, but below or equal to uptake in the liver

4-uptake slightly to moderately higher than liver

5-markedly increased uptake or any new lesion

New sites of FDG-avidity felt unrelated to lymphoma (Deauville 3 or less) will be considered CR but imaging should be repeated 6-8 weeks later to insure resolution of inflammatory changes.

2. Variably FDG-avid or PET negative prior to therapy: regression to normal size on CT (≤ 1.5 cm in their greatest transverse diameter for nodes ≥ 1.5 cm before therapy). Previously involved nodes that were 1.1 to 1.5 cm in their greatest transverse diameter before treatment must have decreased to <1 cm in their greatest transverse diameter after treatment, or by more than 75% in the sum of the products of the greatest diameters (SPD).
3. The spleen, if considered to be enlarged before therapy on the basis of a CT scan, must have regressed in size and must not be palpable on physical examination.

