11.5.2 Partial Response (PR)

1. $\geq 50\%$ decrease in SPD of up to 6 largest dominant masses
 - a. FDG-avid or PET positive prior to therapy: one or more PET positive at previously involved site with a Deauville score >3
 - b. Variably FDG-avid or PET negative: regression on CT
2. No new sites of disease or increase in the size of the other nodes, liver, or spleen.
3. Splenic and hepatic nodules must regress by at least 50% in the SPD.

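### A new lesion counts as progression in 11.5.4 only if PET positive, yet scheduled follow-up is CT only and no event date is fixed, so duration of response and PFS can read too long

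*Combined protocol and SAP*

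**What the plan says.** **Definition.** The new-lesion route to progressive or relapsed disease in 11.5.4 is "Appearance of a new PET positive (Deauville 4 or 5) lesion(s) > 1.5 cm in any axis". The other routes in 11.5.4 all need growth of nodes or lesions already known, which CT can measure.

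**Schedule.** Item 4 of the visit evaluation schedule, after 10.4, limits PET to three time points: "PET/CT Scan will be performed at baseline, 6 weeks after completion of the first cycle, and 6 weeks after completion of the second cycle". It continues: "Staging will then be performed with CT scans of the chest, abdomen, and pelvis every 6 months for the first 2 years", then yearly. Section 10.3 agrees ("Contrast enhanced CT scan of the chest, abdomen, and pelvis with tumor measurements will be performed every 6 months"), as does 11.1 ("Patients who continue on study (non-progressors) after 2 cycles will be assessed using a CT scan").

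**CT branches elsewhere.** The response categories allow for disease that PET does not show reliably. For CR, 11.5.1 has "Variably FDG-avid or PET negative prior to therapy: regression to normal size on CT"; for PR, 11.5.2 has "Variably FDG-avid or PET negative: regression on CT"; SD in 11.5.3 has a similar clause. The new-lesion rule in 11.5.4 has none.

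**Endpoints.** Duration of response (11.6) ends when recurrence or progression is objectively documented. PFS (11.7) ends at documented progression or death. These are the two efficacy endpoints named in the secondary objectives (1.3).

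**The concern.** The new-lesion rule calls for a PET result in the years when the protocol schedules no PET. No section requires PET or biopsy when a follow-up CT shows a new lesion, and none says whether the event takes the date of that CT, of a later PET, or of later growth.

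Such a subject may also fit no category. PR requires "No new sites of disease or increase in the size of the other nodes, liver, or spleen", and for FDG-avid disease SD also excludes new sites, whether seen on CT or PET. In variably avid or PET-negative disease, SD asks only that earlier lesions be unchanged on CT, so a subject with a new lesion could still be recorded as stable. In that disease even an unscheduled PET might never satisfy 11.5.4.

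At stake is the dating of relapses first seen as new lesions. They can be recorded late and occasionally not at all. The error runs one way: duration of response and PFS read too long.

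**Working it through.** **1. Definition against schedule**

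| Period | Scheduled imaging | Growth of known disease | New lesion |
|---|---|---|---|
| After cycle 1 and after cycle 2 | PET-CT | Assessable | Assessable if FDG-avid; no rule if not avid |
| Follow-up to year 5 | CT only | Assessable | Needs a PET that is not scheduled |

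**2. What is not affected.** The plan gives no figure for relapse dating. Its only design figures are those of the Simon test in 13.2: 13 subjects, continue with at least 6 responses, then 15 more, success with at least 15 of 28. With X1 and X2 binomial on 13 and 15 subjects, P(success) is the sum over x = 6 to 13 of P(X1 = x) × P(X2 ≥ 15 − x). This gives 0.0930 at 40% (stated 0.093) and 0.9035 at 65% (stated 0.904). Early stopping, P(X1 ≤ 5), is 0.574 and 0.046 (stated 0.57 and 0.05). All reproduce. The CT-only period begins after the end-of-treatment PET-CT, so it does not enter this test.

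**3. Inputs for an illustration of size**
- Median duration of response m = 26 months (2.3), taken as exponential: S(t) = 0.5^(t/m). The exponential form is an assumption.
- Clock from the end-of-treatment scan; CT at 6, 12, 18, 24, 36, 48 and 60 months (10.3). No censoring before 60 months (assumption).
- Share f of relapses first seen as new lesions: not in the documents; 20% to 40% assumed.
- 18 responders: 0.65 × 28 = 18.2, using the alternative in 13.2.

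S(18) = 0.6189, S(24) = 0.5274, S(36) = 0.3830, S(48) = 0.2781, S(60) = 0.2020.

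**4. A PET is done d months after the CT, and the event takes the PET date.** Relapses found at scans up to month 48 each gain d months within the 60-month window, so the mean event-free time rises by f × d × (1 − S(48)).
- f = 0.2, d = 1: 0.2 × 1 × 0.7219 = 0.14 months.
- f = 0.4, d = 2: 0.4 × 2 × 0.7219 = 0.58 months.

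**5. Worst case: no work-up, event recorded at the next scheduled CT.** The value read at scan k is (1 − f) × S(t_k) + f × S(t_(k−1)).

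| | f = 0 | f = 0.2 | f = 0.4 |
|---|---|---|---|
| Event-free at 24 months | 52.7% | 54.6% | 56.4% |
| Event-free at 36 months | 38.3% | 41.2% | 44.1% |
| Mean event-free time to 60 months | 33.4 | 34.7 | 36.0 |
| Scan-dated median (months) | 36 | 36 | 36 |

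For example, at 24 months with f = 0.4: 0.6 × 0.5274 + 0.4 × 0.6189 = 0.5640. The mean is the area under the scan-dated step curve.

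Counts: 18 × (1 − 0.2020) = 14.4 relapses by 60 months. Of these, 14.4 × f = 2.9 to 5.7 are dated 6 or 12 months late or not seen by month 60. The not-seen part is 18 × (0.2781 − 0.2020) × f = 0.3 to 0.5.

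**6. Scale.** The standard error at 24 months is sqrt(0.5274 × 0.4726 / 18) = 0.118. One responder is 1/18 = 5.6 points. The worst-case shift at 24 months is 1.8 to 3.7 points.

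**The case against.** **The protocol's own scale may cover the case.** The Deauville list in 11.5.1 puts a newly appearing lesion under score 5, and 11.5.4 accepts a score of 5. Section 11.1 also says progression will be judged by the cited 2014 criteria. This stands in part. A reader might infer that a new CT lesion is simply not progression as written; the documents do not support so flat a statement. They do not settle the opposite either: Deauville is a PET score, 11.5.4 separately demands PET positivity, and the cited source cannot be consulted here. What remains is ambiguity in a rule that should have one reading.

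**The endpoint definitions are broad.** Sections 11.6 and 11.7 do not mention PET, and nothing forbids an unscheduled PET or a biopsy. True, but nothing requires one either, so both the event and its date depend on local practice.

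**The worst case is severe and its effect small.** It assumes no work-up of any new-lesion relapse, an assumed share and full follow-up. The shift at 24 months is still less than one responder and well inside the standard error. This stands, and limits the weight of the point.

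**Conclusion.** The gap is real. The new-lesion rule depends on PET, scheduled follow-up is CT only, there is no CT branch for non-avid disease, and no date is fixed. Relapses first seen as new lesions can be dated late, or occasionally missed, and the error always lengthens duration of response and PFS.

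The effect is modest: 0.1 to 0.6 months on a 60-month mean of about 33.4 if a PET follows promptly, and 1.8 to 3.7 points at 24 months if nothing is done until the next scan. These figures rest on the assumed 20% to 40% share, an exponential curve with median 26 months and, for the standard error and counts, 18 responders.

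Two stronger readings should be resisted. A reader might infer that the median duration of response is inflated. At a true median of 26 months the scan-dated median stays at 36 months in every scenario in step 5. A shift does appear at a true median of 12 months, but only because a scan then falls exactly on the median. A reader might also infer that the trial's main conclusion is at risk; the CT-only period does not touch the Simon test. The change should be made because it is cheap and the bias has one direction.

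**What to change.** In 11.5.4, add a CT branch for new lesions. It should cover the CT-only follow-up period, and variably FDG-avid or PET-negative disease at any assessment. Suggested content: a new lesion over 1.5 cm in any axis on CT, attributed to lymphoma, is progressive or relapsed disease, dated to the first scan that shows it, unless PET or biopsy, if done, shows that it is unrelated to lymphoma. In 11.6 and 11.7, refer to that date.

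The cost is one criterion and one dating sentence in each of two sections, with no added scans. The downside is a small risk of counting a non-lymphoma lesion as an event, limited by the exception. Because progression also ends protocol therapy (5.4), the investigators should agree the wording that applies at the restaging after cycle 1.

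As a separate, minor point, reconcile the follow-up statements. Section 10.4 gives 1 year for duration of response, and 1.1 and 5.1 speak of CT follow-up for responders. Sections 10.3, 11.1, 13.2 and the visit evaluation schedule follow subjects without progression to 5 years. Survival follow-up in 5.5 concerns subjects taken off therapy and does not conflict with these.

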11.6 Duration of Response

Duration of overall response: The duration of overall response is measured from the time measurement criteria are met for CR or PR (whichever is first recorded) until the first date that recurrent or progressive disease is objectively documented (taking as reference for progressive disease the smallest measurements recorded since the treatment started).

The duration of overall CR is measured from the time measurement criteria are first met for CR until the first date that recurrent disease is objectively documented.

Duration of stable disease: Stable disease is measured from the start of the treatment until the criteria for progression are met, taking as reference the smallest measurements recorded since the treatment started.

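### After a PET-defined complete response, uptake returning at a prior site without growth is no event under 11.5.4, so CR duration, DOR and PFS run on

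*Combined protocol and SAP*

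**What the plan says.** All references are to the combined protocol and SAP.

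- **CR (11.5.1).** Item 1, for disease PET positive before therapy: "mass of any size permitted if PET negative with a score of 3 or less on the Deauville five point scale". Item 2 covers the remaining disease and uses CT size: "Variably FDG-avid or PET negative prior to therapy: regression to normal size on CT".
- **PR (11.5.2).** SPD down by at least 50%, with, for avid disease, "one or more PET positive at previously involved site with a Deauville score >3", and no new sites or growth elsewhere.
- **SD (11.5.3).** A residual class: "Stable disease is defined as less than a PR (see above) but is not progressive or relapsed disease". Its PET text for avid disease is "PET positive at prior sites of disease and no new sites on CT or PET".
- **PD or RD (11.5.4).** PET enters only through "Appearance of a new PET positive (Deauville 4 or 5) lesion(s) > 1.5 cm in any axis". The other limbs are size limbs: at least 50% in the SPD of more than one node, at least 50% in the longest diameter of a known node, or a more than 50% "increase from nadir in the SPD of any previous lesions". The proviso on uptake thought unrelated to lymphoma concerns new sites only.
- **Clocks (11.6, 11.7).** CR duration is "measured from the time measurement criteria are first met for CR until the first date that recurrent disease is objectively documented". DOR ends at recurrent or progressive disease, and PFS at progression or death.
- **Imaging (10.3, 10.4 visit schedule item 4, 11.1).** PET-CT at baseline, 6 weeks after cycle 1 (day 84) and 6 weeks after cycle 2 (day 168 in 11.1). After that, CT only, every 6 months for 2 years and then annually.

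DOR and PFS are secondary endpoints (1.3, 13.1). CR duration is defined in 11.6 but is not listed as an endpoint.

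**The concern.** Remission and relapse at the same site are judged by different measures. Spleen item aside, a PET-positive subject enters CR because uptake has fallen, whatever the mass measures. If uptake then returns at that site, the finding that made the case a CR has reversed, yet no limb of 11.5.4 is met unless the site has also grown by about half. Recurrence is then dated from a later CT. At stake are two secondary endpoints, DOR and PFS, together with CR duration. The error has one direction: an event can be missed or dated late by this gap, but not dated early.

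**Working it through.** **1. The plan's own figures.** Inputs from 13.2: 13 subjects in stage 1, continue with 6 or more responses, 15 more subjects, success at 15 or more of 28.

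P(success) = sum over x = 6 to 13 of P(X = x) × P(Y ≥ 15 − x), with X ~ Bin(13, p) and Y ~ Bin(15, p). P(early stop) = P(X ≤ 5).

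| | p = 0.40 | p = 0.65 |
|---|---|---|
| P(success), computed | 0.0930 | 0.9035 |
| P(success), plan | 0.093 | 0.904 |
| P(early stop), computed | 0.574 | 0.046 |
| P(early stop), plan | 0.57 | 0.05 |

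All reproduce, and none uses the relapse rule.

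**2. Two constructed records under 11.5.1 to 11.5.4.** Each has one node, PET positive at baseline, no new lesion, and all other PR items met. SPD is the product of the two diameters.

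| | Record A | Record B |
|---|---|---|
| Baseline | 40×30 = 1200 mm² | 40×30 = 1200 mm² |
| Day 84, Deauville 2 | 25×20 = 500 | 35×28 = 980 |
| Class at day 84 | CR | CR |
| End of treatment, Deauville 5 | 27×21 = 567 | 36×29 = 1044 |
| SPD change from nadir | 567/500 − 1 = +13.4% | 1044/980 − 1 = +6.5% |
| Longest diameter, change | 27/25 − 1 = +8% | 36/35 − 1 = +2.9% |
| PD or RD? | No | No |
| SPD change from baseline | 567/1200 − 1 = −52.8% | 1044/1200 − 1 = −13% |
| Class at end of treatment | PR | SD |

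Record A meets 11.5.2, and SD is open only to what falls short of PR. Record B falls short of PR and fits the SD text. Neither class stops a clock in 11.6 or 11.7.

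**3. Effect on the clocks.** CR is first met on day 84 and uptake is back on the end-of-treatment scan. The next scheduled scan is a CT 6 months later (10.3), taken as 183 days. No death or unscheduled scan is assumed in between. Section 11.1 puts the end-of-treatment scan at day 168, but day 84 plus a 28-day cycle 2 plus 42 days is 154, so both are shown.

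| End-of-treatment scan | DOR and CR duration if relapse | As written, at least | PFS if relapse | As written, at least |
|---|---|---|---|---|
| Day 168 | 168 − 84 = 84 | 84 + 183 = 267 | 168 | 168 + 183 = 351 |
| Day 154 | 154 − 84 = 70 | 70 + 183 = 253 | 154 | 154 + 183 = 337 |

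**4. Why these are minimums.** The next CT records an event only if growth has passed 50% from nadir. In record A the growth still needed is ln(1.5/1.134)/ln 2 = 0.40 SPD doubling times. For assumed doubling times of 4, 6, 12 and 24 months that is 1.6, 2.4, 4.8 and 9.7 months, so the event is picked up 6, 6, 6 and 12 months late.

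**5. How many subjects.** The documents give no rate for this finding. As a rough ceiling, take the CR share at 60 µg/m²/day in the earlier phase 1 study (2.2.7): 13 of 35 in the text, but 8 of 35 in Table 2-6. For 28 subjects this gives 28 × 13/35 = 10.4 or 28 × 8/35 = 6.4 CRs. If 5%, 10% or 20% (assumed) reverted, 0.5, 1.0 or 2.1 subjects would be affected on the first share, and 0.3, 0.6 or 1.3 on the second. These counts lean high because they treat every CR as present at day 84. The share also covers all NHL types and includes unconfirmed CRs in a study with centrally reviewed CT, so it is not a PET-defined rate in indolent disease.

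**The case against.** **A subject who moves from CR to PR is still a responder.** DOR in 11.6 starts at CR or PR and ends at recurrence or progression, so continuing it through a PR is consistent with its wording. This stands in part. The mismatch is plainest for CR duration, and for record B, where the subject no longer meets either response definition. Scoring returned uptake as relapse would also separate two subjects with identical end-of-treatment scans, one previously in CR and one in PR. That is a choice of criteria, but the plan has not stated it.

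**The cited 2014 response criteria (11.1, 13.1) may fill the gap.** Their content is not in the documents. The protocol writes out its own four categories, and assessors will apply those. If the citation is meant to govern, the protocol should say so.

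**A new PET-positive lesion could mean an old lesion newly positive.** The SD text sets prior sites against new sites, which tells against this.

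**Reach is small.** This stands. Only a subject already in CR at day 84 can show the finding on a scheduled scan, and only at end of treatment. Later cases need an unscheduled PET.

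Several stronger readings are tempting, and the documents do not support them:

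- *A lost CR always becomes SD.* Record A is PR.
- *Returned uptake is never relapse.* With more than 50% growth from nadir, or with a new lesion, it is PD or RD.
- *Every CR is exposed.* Item 2 of 11.5.1 defines CR by CT size for variably avid or PET-negative disease.

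**Conclusion.** The gap is real but narrow. For disease PET positive before therapy, a CR reached at day 84 can reverse at the same site on the end-of-treatment PET-CT, or on an unscheduled PET, without 50% growth or a new lesion, and no event is recorded. The subject is scored PR or SD, and CR duration, DOR and PFS run on by at least about 6 months to the next scheduled CT. The direction follows from the rules; calling the extra time an overstatement rests on treating lost PET remission as recurrence, which is how 11.5.1 itself defines the remission.

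Probably no more than a few of at most 28 subjects are affected. With no rate in the documents, the effect on median DOR or PFS cannot be computed. A reader might infer that the primary result is at risk. That is not shown: 13.2 counts subjects who achieve a response, the design figures do not use the relapse rule, and section 13 sets no test on DOR or PFS. The point should be corrected, but it does not threaten the trial's main conclusion.

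**What to change.** - **11.5.4:** add that, after a CR met under 11.5.1 item 1, return of uptake to Deauville 4 or 5 at a previously involved site, judged to be lymphoma, is relapsed disease dated to that PET-CT.
- **11.5.2 and 11.5.3:** state that a subject who has been in CR is not re-scored PR or SD on that finding. Both sections need this; otherwise record A would be PR and relapse at once.
- **11.6 and 11.7:** refer to the new limb, so that CR duration, DOR and PFS end on the same date.

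If the sponsor prefers relapse at a known site to rest on size alone, the protocol should say so, and reports of DOR and PFS should state it.

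The cost is a few sentences. The PET-CTs are already scheduled, and no extra scan is required. On scheduled scans the finding arises only after both cycles. DOR and PFS become slightly shorter, and assessors must judge whether returned uptake is lymphoma or inflammation.

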11.3 Disease Parameters

Measurable disease. Measurable lesions are defined as those that can be accurately measured in at least one dimension (longest diameter to be recorded) as ≥ 20 mm with conventional techniques (CT, MRI, x-ray) or as ≥ 10 mm with spiral CT scan. All tumor measurements must be recorded in millimeters (or decimal fractions of centimeters).

Non-measurable disease. All other lesions (or sites of disease), including small lesions (longest diameter <20 mm with conventional techniques or <10 mm using spiral CT scan), are considered non-measurable disease. Bone lesions, leptomeningeal disease, ascites, pleural/pericardial effusions, lymphangitis cutis/pulmonis, inflammatory breast disease, abdominal masses (not followed by CT or MRI), and cystic lesions are all non-measurable.

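### The SPD progression rules in 11.5.4 have no minimum lesion size, so small growth in a node still of normal size can end PFS and duration of response too early

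*Combined protocol and SAP*

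**What the plan says.** Section 11.5.4 lists several routes to progression.

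- **Item 1, new lesions:** PET-positive "lesion(s) > 1.5 cm in any axis". This has a size floor.
- **Item 1, single node:** a 50% or greater "increase in longest diameter of a previously identified node > 1 cm in short axis". This also has a floor.
- **Item 1, several nodes:** a 50% or greater increase in the SPD of more than one node. No floor clearly attaches to it.
- **Item 2:** a rise of more than 50% "increase from nadir in the SPD of any previous lesions". It states no minimum size and no minimum absolute increase.

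Section 11.5.1 sets the size limits for CR when disease was variably FDG-avid or PET-negative before therapy. It asks for "regression to normal size on CT", meaning at most 1.5 cm for nodes that were at least 1.5 cm. Nodes that were 1.1 to 1.5 cm "must have decreased to <1 cm in their greatest transverse diameter after treatment", or must shrink by more than 75% in SPD. For disease PET-positive before therapy, a PET-negative mass of any size is allowed.

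Section 11.3 says that lesions under 10 mm on spiral CT "are considered non-measurable disease", but 11.5.4 does not refer to that limit. Section 11.6 ends duration of response at documented recurrence or progression, "taking as reference for progressive disease the smallest measurements recorded since the treatment started". Section 11.7 ends PFS at documented progression or death. Scheduled imaging after the end-of-treatment PET-CT is by CT only (10.3 and 11.1).

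**The concern.** Item 2 undercuts item 1. A single node must exceed 1 cm in short axis before growth in its longest diameter counts, yet the same node can be PD under item 2 at any size. The size at which 11.5.4 declares progression then overlaps the size that 11.5.1 accepts as normal, so one CT can support both continuing CR and PD.

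The overlap matters most in follow-up. The reference is the smallest measurement so far, so subjects whose nodes shrank most have the lowest threshold in millimetres. Each further CT is another chance to cross it, and the first crossing fixes the event date. In a node that is truly stable, measurement error can therefore only bring the event forward. With at most 28 subjects, a few misdated events would visibly shift the PFS and duration-of-response estimates.

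**Working it through.** **Design figures first.** An exact two-stage binomial calculation (13 subjects, continue with 6 or more responses; 28 in total, success with 15 or more) gives alpha 0.0930, power 0.9035, and early-stopping probabilities 0.574 and 0.046. Section 13.2 states 0.093, 0.904, 0.57 and 0.05. They agree, and none of them depends on the PD rule.

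**When does item 2 trigger?** For one node, change = (L2 x S2)/(L1 x S1) - 1. Equal growth in both diameters passes 50% once each grows by a factor above √1.5 = 1.225.

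| Nadir (mm) | Later (mm) | Products (mm²) | Change | Over 50%? |
|---|---|---|---|---|
| 8 x 8 | 10 x 10 | 64 to 100 | +56% | yes |
| 9 x 8 | 11 x 10 | 72 to 110 | +53% | yes |
| 10 x 6 | 12 x 8 | 60 to 96 | +60% | yes |
| 12 x 10 | 14 x 13 | 120 to 182 | +52% | yes |
| 9 x 9 | 11 x 11 | 81 to 121 | +49.4% | no |
| 10 x 10 | 12 x 12 | 100 to 144 | +44% | no |
| 8 x 8 | 10 x 8 | 64 to 80 | +25% | no |

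Every node in the table ends at or below 15 mm. The 10 x 6 and 12 x 10 rows show that applying the 10 mm measurability limit of 11.3 would not remove the overlap.

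For a square node, 2 mm in both diameters is enough only if the nadir is below 2/(1.225 - 1), about 8.9 mm. Without the 2 mm limit, a square nadir of up to 15/1.225, about 12.2 mm, can pass 50% and still be within 1.5 cm.

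**Per lesion or summed?** If one 8 x 8 mm node grows to 10 x 10 mm among k equal nodes, the summed change is 36/(64k): 56% for k = 1, 28% for k = 2, 19% for k = 3 and 9% for k = 6. If all the nodes grow alike it stays at 56%. Item 2 does not say which reading applies.

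**How often could error alone trigger it?** The documents give no measurement error, so this is a simulation under assumptions. The node is truly stable. Each diameter carries independent Gaussian error and is rounded to the millimetre. There is one post-treatment scan and then follow-up CTs, and PD is a product above 1.5 times the running minimum. Seven CTs is the full schedule in 10.3 (months 6, 12, 18, 24, 36, 48 and 60). Four is the number falling within the 26-month median response duration cited in 2.3.

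| Case | CTs | SD 0.5 mm | SD 1.0 mm | SD 1.5 mm |
|---|---|---|---|---|
| One 9 x 8 node | 7 | 2% | 51% | 84% |
| One 9 x 8 node | 4 | about 1% | 28% | - |
| One 12 x 10 node | 7 | 0.1% | 24% | 67% |
| One 12 x 10 node | 4 | about 0% | 11% | - |
| Three 9 x 8 nodes, summed | 7 / 4 | - | 5% / 2% | - |
| Three 12 x 10 nodes, summed | 7 / 4 | - | 0.3 to 0.4% / 0.1% | - |

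Three nodes judged singly at SD 1.0 mm with seven CTs give 88% (9 x 8) and about 56% (12 x 10). A dash means that no figure is reported for that cell.

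**The case against.** **The summed reading is the more natural one.** Section 11.5.1 spells out SPD as a sum of products, and item 2 speaks of lesions in the plural. Summed over three nodes at SD 1.0 mm, the risk is a few per cent or less. This stands as a limit on size. It does not settle the text, and it gives no protection where a single lesion is followed or all lesions move together.

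**Response criteria are adopted by citation.** Section 11.1 cites published lymphoma criteria that might contain a floor. But 11.5.4 writes out its own rule, and a reader applying it as written finds none in item 2.

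**A floor has its own bias.** Real regrowth from 7 x 7 to 14 x 14 mm (49 to 196 mm², +300%) would not count until the node passed 1.5 cm, so PFS could be dated late. This is fair and is counted as a cost.

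**Stronger readings that the documents do not support:**

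- *Any 2 mm change is progression.* It is not. The growth must be in both diameters, the nadir must be small or the node narrow, and SPD must be judged per lesion (or there is one lesion, or all grow).
- *Subjects would wrongly lose cycle 2 or be counted as non-responders.* No scan is scheduled between baseline and the pre-cycle-2 scan, so the nadir there is baseline. Entry requires disease of at least 1.5 cm, and up to three of the largest lesions are measured. Only an already small secondary node could trigger the rule at that scan.
- *Slices of up to 10 mm make the measurements unreliable.* Section 11.4 goes on to specify 5 mm reconstruction for spiral CT.

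**Conclusion.** The point holds as a gap in the definition of two secondary endpoints. Item 2 has no size floor and bypasses the single-node floor in item 1. It lets a node of normal size under 11.5.1 be recorded as PD during CT follow-up. The multi-node SPD clause of item 1 shares the gap. The likely direction of error is towards PFS and duration of response ending too early.

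The size is not established. The simulated range for one stable node (about 1% to 84% for 9 x 8 mm, about 0% to 67% for 12 x 10 mm) rests on an assumed error SD and an assumed number of CTs. The share of responders with such nodes is also unknown. A reader might infer that PFS will be badly biased, but the documents show only that the rule allows it. The conflict with the 1.5 cm limit applies to nodes that were at least 1.5 cm before therapy; smaller nodes face the stricter CR limit. The change is worth making because it is cheap and the rule as written can give a wrong event date.

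**What to change.** In 11.5.4:

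1. State whether SPD is judged per lesion or summed over the followed lesions.
2. For both SPD clauses (item 2, and item 1's clause on more than one node), count the rise from nadir as PD only if at least one contributing node or lesion is then above 1.5 cm in longest diameter. That is the protocol's own cut-off for a new lesion and for normal node size.
3. Reconcile this floor with the CR limit of under 1 cm for nodes that were 1.1 to 1.5 cm before therapy. Otherwise a 14 x 14 mm node that shrank to 9 x 9 mm could return to its starting size (196/81 = 2.42, +142%) without counting. For the same reason, do not add a general statement that nodes up to 1.5 cm in a subject in CR are never relapse.

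Borrowing item 1's floor of 1 cm short axis would not be enough: 10 x 10 to 12.3 x 12.3 mm is +51% and still within 1.5 cm. With the 1.5 cm floor and seven CTs, simulated false PD falls to about 0% for one 9 x 8 mm node, and to 0%, 0.1% and 4% for one 12 x 10 mm node at SD 0.5, 1.0 and 1.5 mm.

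The cost is a few sentences, with no change to sample size, alpha or power. The downside is that a true relapse in a small node may be dated one scan later, which is 6 months in the first two years and 12 months after that.
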